## Statistical Analysis Plan

### 7. DEMOGRAPHIC, OTHER BASELINE CHARACTERISTICS, AND MEDICATION

#### 7.1. SUBJECT DISPOSITION AND WITHDRAWALS

##### 7.1.1. Subject Disposition

The number of screened subjects who participated in the MTT and MTT status (negative [passed], positive [failed], or incomplete) will be presented for the MTT set. Percentages will be based on the number of subjects participating in the MTT.

The number and percentage of subjects randomized, not randomized, and treated in the trial will be presented, together with the number and percentage of subjects randomized in each center within each country, and the number and percentage of subjects included in each of the analysis sets. Percentages will be based on the number of subjects randomized.

##### 7.1.2. Withdrawal from the Trial

The number and percentage of randomized subjects who completed the trial and who withdrew from the trial early, including a breakdown of the corresponding reasons for withdrawal, will be presented for the ITT set. All reasons for withdrawal listed in the CRF will be included in the summary, whether or not any subjects withdrew for each reason.

Time to withdrawal from the trial in days will be calculated as:

$$\text{Time} = (\text{date of withdrawal from the trial}) - (\text{date of Trial Day 1}) + 1$$

A Kaplan-Meier plot of time to withdrawal from the trial for the ITT set will be presented. Subjects who do not withdraw will be censored at the date of last participation in the trial. The number of subjects who withdraw and who are censored will be summarized. Kaplan-Meier product limit estimators of the survivor function (probability of staying in the trial) will be summarized for 25th percentile, median, and 75th percentile, and their 95% CIs.

For the study periods [0-6) weeks, [6-14) weeks, [14-26) weeks, [26-31) weeks, and [31-∞) weeks, the number of subjects in the trial at the beginning of the period, the cumulative number of withdrawn subjects at the end of the period, and the probability of withdrawal at the end of the period with the associated 95% CIs will be presented for the ITT set.

## Statistical Analysis Plan

The number and percentage of subjects in categories of time to withdrawal {[0-2) weeks, [2-4) weeks, [4-8) weeks, etc. in 4 weekly intervals} and the number and percentage of subjects withdrawing between each visit will also be presented for the ITT set.

In addition, the follow-up duration will be summarized for the ITT set using summary statistics for continuous variables and also for categorical variables using monthly categories (i.e. 0-1, >1-2, etc.). This will be calculated as:

$$\text{Follow-up duration (months)} = ([\text{last participation date}] - [\text{date of Trial Day 1}] + 1) \times 12 / 365.25$$

Follow-up duration in months will be rounded to one decimal place for displaying purposes.

The number of subjects who attended Visits 2, 3, and 4 will be summarized for the ITT set using summary statistics for categorical variables.

### 7.1.3. Discontinuation from Trial Medication

The number and percentage of subjects who completed the trial on trial medication will be presented for the ITT set.

The number and percentage of subjects who discontinued from trial medication (whether or not they continued in the trial), including a breakdown of the corresponding reasons for discontinuation will be presented for the ITT set. If reason for discontinuation is missing for subjects who withdrew from the trial at the same time as trial medication discontinuation, the reason for withdrawal will be used. In addition, the number and percentage of subjects who discontinued trial medication without off-trial medication efficacy data and the number and percentage of subjects who discontinued trial medication with off-trial medication efficacy data, including a breakdown of the corresponding reasons for discontinuation will be presented for the ITT set. In each case, all reasons for discontinuation listed in the CRF will be included in the summary, whether or not any subjects discontinued for each reason.

For those subjects with off-trial medication efficacy data, the number and percentage of subjects who went on to complete the trial while off trial medication and the number and percentage of subjects who subsequently withdrew early from the trial while off trial medication will be presented for the ITT set.

If applicable, a similar breakdown for subjects who never started trial medication will be presented for the ITT set.

Pharmaxis Ltd

DPM-CF-303

Final v1.0

## Statistical Analysis Plan

Time to discontinuation from trial medication in days will be calculated for subjects receiving at least one dose of trial medication as:

$$\text{Time} = (\text{date of discontinuation from trial medication}) - (\text{date of Treatment Day 1}) + 1$$

Subjects not starting trial medication will have a time to discontinuation of 0 (not censored). Subjects who do not discontinue will be censored at the date of last dose in the trial.

A Kaplan-Meier plot of time to discontinuation from trial medication for the ITT set will be presented. The number of subjects with an event and censored will be summarized. Kaplan-Meier product limit estimators of the survivor function (probability of staying event free) will be summarized for 25th percentile, median, and 75th percentile, and their 95% CIs.

For the study periods [0-6) weeks, [6-14) weeks, [14-26) weeks, [26-31) weeks, and [31-∞) weeks, the number of subjects in the trial at the beginning of the period, the cumulative number of discontinued subjects at the end of the period, and the probability of discontinuation at the end of the period with the associated 95% CIs will be presented for the ITT set.

The number and percentage of subjects in categories of time to discontinuation {[0-2) weeks, [2-4) weeks, [4-8) weeks, etc. in 4 weekly intervals} and the number and percentage of subjects discontinuing between each visit will also be presented for the ITT set.

### 7.2. DEMOGRAPHIC AND OTHER BASELINE CHARACTERISTICS

Demography (gender, race, ethnicity, country, age [years] at screening, weight [kg] at screening and height [cm] at screening), percent predicted FEV1 at screening, percent predicted FEV1 at screening cut points (>90%, >80% to ≤90%, >70% to ≤80%, >40% to ≤70%, and ≤40%), disease severity (percent predicted FEV1 at baseline), and disease severity (percent predicted FEV1 at baseline) cut points (>90%, >80% to ≤90%, >70% to ≤80%, >40% to ≤70%, and ≤40%) will be summarized for the ITT, PP, and SAF sets, and also for the subset of the MTT set who did not go on to be randomized (with the exception of the disease severity at baseline variables). Age, weight, and height will be summarized using summary statistics for continuous variables. Gender, race, ethnicity, and country will be summarized using summary statistics for categorical variables.

$$\text{Age at screening} = (\text{date of MTT} - \text{date of birth} + 1) / 365.25 \text{ truncated to complete years.}$$

Note that due to patient confidentiality regulations in Hungary, it is only possible to collect the year of birth for each subject in that country. In the trial database, the day

## Statistical Analysis Plan

and month of birth will be recorded as 31st December for all Hungarian subjects, therefore age values will be an underestimation.

Screening medications will be summarized for the ITT set, and for the subset of the MTT set who did not go on to be randomized, by anatomical main group, therapeutic subgroup and preferred drug name terms using summary statistics for categorical variables. Screening medications are defined in Section 7.7.2. A subject who took more than one screening medication will be counted only once if these medications belong to the same anatomical main group, therapeutic subgroup or preferred drug name. Tables will be sorted alphabetically by anatomical main group, therapeutic subgroup and preferred drug name.

Screening sputum qualitative microbiology data will be summarized for the ITT set using summary statistics for categorical variables. Clinically significant screening laboratory tests, screening sputum qualitative microbiology, and screening urine pregnancy test data will be listed.

### 7.3. PRIMARY DIAGNOSIS

The primary diagnosis information collected at screening will be summarized for the ITT and SAF sets, and also for the subset of the MTT set who did not go on to be randomized. This will include time since diagnosis (years), age at diagnosis (years), cystic fibrosis transmembrane conductance regulator (CFTR) mutation (both deltaF508, one deltaF508, at least one other known mutation, and both unknown), use of rhDNase, previous diagnosis of bronchiectasis, number of hospitalizations in last 12 months due to PE, number of PEs treated with IV antibiotics in last 12 months, previous hypertonic saline use, and hypertonic saline use at screening.

Time since diagnosis (years) and age at diagnosis (years), will be summarized using summary statistics for continuous variables. All other endpoints will be summarized using summary statistics for categorical variables. Appropriate categories will be defined based on available data for number of hospitalizations in last 12 months due to PE and number of PEs treated with IV antibiotics in last 12 months.

Time since diagnosis will be calculated as:

$$\text{Time since diagnosis} = (\text{age at screening} - \text{age at diagnosis})$$

where age at diagnosis = (date of first diagnosis - date of birth + 1) / 365.25 truncated to complete years.

If date of first diagnosis is partially missing, the most conservative case will be considered when calculating time since diagnosis: if a partial date is missing a start day,

## Statistical Analysis Plan

'01' will be used for the day; if a partial date is missing a month, 'January' will be used for the start month. If date of first diagnosis is fully missing, the value of age at diagnosis as recorded on the CRF will be used in the above calculation.

If both date of first diagnosis and age at diagnosis (CRF) are missing, then the derived age at diagnosis and time since diagnosis will be missing.

### 7.4. HEMOPTYSIS HISTORY

Hemoptysis history will be summarized for the ITT and SAF sets. This will include the number and percentage of subjects with a history of hemoptysis, and for those subjects, the type of event (single or multiple), the incidence of any hemoptysis events not concurrent with an exacerbation, and the incidence of any massive hemoptysis events (defined as acute bleeding  $\geq 240$  mL in a 24-hour period and/or recurrent bleeding  $\geq 100$  mL per day over several days). For those subjects experiencing a massive hemoptysis, the number and percentage of subjects with all massive hemoptysis concurrent with an exacerbation, the number and percentage of subjects with at least one massive hemoptysis not concurrent with an exacerbation, and the time of the most recent massive hemoptysis (within the last 12 months or more than 12 months ago) will be summarized.

### 7.5. MEDICAL HISTORY AND CONCOMITANT DISEASES

Medical history and concomitant diseases will be coded using Medical Dictionary for Regulatory Activities (MedDRA) Version 11.1.

Medical history will be defined as any clinically significant past medical conditions that ended before screening. Medical history will be summarized for the ITT and SAF sets with number and percentage of subjects with at least one medical history item, and number and percentage of subjects by system organ class (SOC) and preferred term (PT). The terms will be sorted alphabetically by SOC and PT.

Concomitant diseases will be defined as any clinically significant current medical conditions that were ongoing at screening. Concomitant diseases will be summarized for the ITT and SAF sets with number and percentage of subjects with at least one concomitant disease, and number and percentage of subjects by system organ class (SOC) and preferred term (PT). The terms will be sorted alphabetically by SOC and PT.

Concomitant diseases will be flagged on the medical history and concomitant diseases data listing.

## Statistical Analysis Plan

### 7.6. RESPONSE TO SCREENING MANNITOL TOLERANCE TEST

The MTT parameters FEV1 and oxygen saturation (SpO2) will be summarized by timepoint and by MTT result (negative [passed], positive [failed], and incomplete) for the MTT set. In addition the maximum percentage fall in FEV1 and greatest absolute drop in SpO2, from the 40 mg, 120 mg, 240 mg and 400 mg doses attempted, will be summarized by MTT result (negative, positive, and incomplete) for the MTT set.

Percentage fall in FEV1 will be calculated as:

$$\text{Percentage fall in FEV}_1 = 100 \times ((\text{Baseline FEV}_1 - \text{post Baseline FEV}_1) / \text{Baseline FEV}_1)$$

Percentage fall in FEV1 will be rounded to two decimal places for displaying purposes.

Absolute drop in SpO2 will be calculated as:

$$\text{Absolute drop in SpO}_2 = \text{Baseline SpO}_2 - \text{post Baseline SpO}_2$$

### 7.7. MEDICATION

Prior and concomitant medications will be coded using WHO Drug Dictionary version DD B2 March 2010. Medication will be presented by anatomical main group (ATC Level 1), therapeutic subgroup (ATC Level 2) and preferred drug name. If anatomical main group, therapeutic subgroup or preferred drug name is unavailable, "uncoded" will be used. A subject who took more than one medication will be counted only once if these medications belong to the same anatomical main group, therapeutic subgroup or preferred drug name. Tables will be sorted alphabetically by anatomical main group, therapeutic subgroup and preferred drug name.

If either the start or stop date of medication is missing, the most conservative case will be considered when assigning medications to categories: for a missing start date (where stop date is after date of Trial Day 1) the date will be imputed as the date of Trial Day 1; for a missing stop date the date will be imputed as the date of last participation in the trial. If a partial date is recorded, the following convention will be used to assign the medication:

- If a partial date is missing a start day, '01' will be used for the day; if a start date is missing a month, 'January' will be used for the start month.
- If a partial date is missing a stop day, last day of the given month will be used for the stop day; if a stop date is missing a month 'December' will be used for the stop month.

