## Statistical Analysis Plan

- Change in sputum production (volume, color, consistency).
- Increased dyspnea.
- New or increased hemoptysis.
- Malaise, fatigue, or lethargy.
- Fever ( $\geq 38$  °C).
- Anorexia or weight loss.
- Sinus pain or tenderness.
- Change in sinus discharge.
- FVC or FEV1 decreased by >10% from previous recorded value.
- Radiographic signs indicative of pulmonary infection.
- Increased cough.
- Changes in physical examination of the chest.

PDPEs will be identified from the pulmonary exacerbation (PE) Review CRF page, where IV antibiotics were recorded as being given for a PE and, in addition, 4 or more of the above signs or symptoms were ticked.

Time to first PE will also be calculated, in a similar manner, and explored under this endpoint, however the hierarchical testing will be based on time to first PDPE. A PE is defined as any event recorded on the PE Review CRF page that has associated antibiotic use (oral, inhaled, or IV), whether or not it meets the above conditions.

- 3) Number of days on antibiotics (oral, inhaled, or IV) due to PDPE\*\* over the 26-week treatment period. Medication use for a PE will be identified on the concomitant medication page by a yes/no box; a further check will be made to ensure medications are for a PDPE (i.e. that the PE event to which the medication is linked satisfies the above criteria for a PDPE). It will also be checked that both the PDPE and the medication use started on or after Trial Day 1 (defined in Section 6.2.2). Antibiotics are identified by their Anatomical Therapeutic Chemical (ATC) Level 2 code J01 (antibacterials for systemic use).

Number of days on one antibiotic = stop date-start date+1

The number of days for all occurrences will be summed. If multiple antibiotics are received for the same event, the durations will be computed separately and added together. If an antibiotic is ongoing at the end of the subject's participation in the trial, the subject's date of last participation in the trial will be used in the calculation instead of the stop date.

Date of last participation in the trial is defined in Section 6.2.5.

\*Updated in this SAP to be reported in L rather than mL to match the units used in data collection (see Section 11).

\*\*Clarified in this SAP that pulmonary exacerbations classified as protocol defined pulmonary exacerbations (PDPEs) will be used in the main analyses for these endpoints (see Section 11).

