## Statistical Analysis Plan

### 6.3. MISSING DATA

Missing or partial dates will be resolved in the most conservative manner. Additional details regarding partial or missing dates for the different safety data are given in Sections 6.2.1, 7 and 9 where applicable.

Details of imputation of missing values for efficacy endpoints are given in Section 8. Subjects who discontinue trial medication should remain in the trial and continue to provide all scheduled measurements. While all efforts will be made to ensure subjects remain in the trial, the following planned imputation strategy will allow for appropriate analyses of FEV1, FVC, ease of expectoration VAS score, and CFQ-R respiratory domain in the presence of missing data.

To calculate baseline values, missing Visit 1 measurements will be replaced by Visit 0 (screening) measurements, if available.

Missing post-baseline measurements as a result of withdrawal from the trial will be imputed in both ITT and PP analyses using an imputation using dropout reason (IUDR) methodology. For subjects who withdraw from the trial due to AE, death, physician decision, or lack of efficacy, missing post-baseline measures as a result of withdrawal from the trial will be imputed using the baseline measurement (baseline observation carried forward [BOCF] procedure). Missing measurements as a result of other causes of withdrawal from the trial (i.e. lost to follow-up, relocation, pregnancy, major protocol deviation, sponsor decision, withdrawal of consent, or other) will not be imputed. Missing data at intermediate visits (i.e. where data is available at a later visit) will not be imputed. Any measurements excluded from the PP analysis at the BDRM, and any derived variables based on these excluded measurements, will be treated as missing data but will not be included in the imputation process.

Imputation of missing FEV1 measurements by means of BOCF is a reasonable assumption in studies of adult subjects with CF, as those subjects who withdraw from the trial will no longer receive trial medication and are thus likely to promptly return to their baseline lung function. Imputation by BOCF specifically inhibits any assumed prolongation of an observed early trial medication benefit implicitly conferred by a mixed model.

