### 9.3. ADVERSE EVENTS

AEs will be coded using MedDRA v11.1.

AEs will be considered MTT-emergent if they started within 2 days after MTT (MTT day and the day after) but before Treatment Day 1.

AEs will be considered treatment-emergent unless there is clear indication that the event occurred prior to Treatment Day 1 (i.e. AEs starting on Treatment Day 1 will be assumed to have occurred after the first dose of trial medication) or the start date is >28 days after permanent discontinuation of trial medication. MEAEs cannot be treatment-emergent AEs (TEAEs) unless they worsen on or after Treatment Day 1. AEs present prior to Treatment Day 1 that increased in intensity or relationship to trial medication while the subject was on trial medication or within 28 days of permanent discontinuation from trial medication will be classed as TEAE. Events with missing or partial dates will be handled such that in the absence of contradictory information an AE is treatment-emergent. So for a missing start date (where stop date is after date of Treatment Day 1) the date will be imputed as the date of Treatment Day 1; for a missing stop date the date will be imputed as the date of last participation in the trial. If a partial date is recorded, the following convention will be used to assign the AE:

- If a partial date is missing a start day and month/year is the same as the date of Treatment Day 1 then use the date of Treatment Day 1, else '01' will be used for the day; if a start date is missing a month and the year is the same as the date of Treatment Day 1 then use the date of Treatment Day 1, else January will be used for the start month.
- If a partial date is missing a stop day and month/year is same as last participation date then use last participation date, else last day of the given month will be used for the stop day; if a stop date is missing a month and year is the same as last participation date then use last participation date, else December will be used for the stop month.

AEs will be summarized by SOC and PT. Subjects will be counted once at the SOC level and once at each PT within the SOC level. Where applicable, summaries will include number and percentage of subjects who report at least one AE, number and percentage of subjects reporting at least one AE in a SOC, number and percentage of subjects reporting at least one AE in a PT, and total number of events within a SOC and within a

Pharmaxis Ltd

DPM-CF-303

Final v1.0

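### SAP 7.7 bounds fully missing medication dates but not partial ones, so an exacerbation antibiotic with a partly known start can be dropped from the third hierarchical endpoint while one with no start date is kept

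*SAP*

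**What the plan says.** SAP 4.2.1 item 3 defines the third hierarchical secondary endpoint, days on antibiotics due to PDPE. For inclusion: "It will also be checked that both the PDPE and the medication use started on or after Trial Day 1". For duration: "Number of days on one antibiotic = stop date-start date+1", summed over antibiotics. If an antibiotic is ongoing when participation ends, the last participation date replaces the stop date.

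SAP 7.7 is the only readable rule for incomplete medication dates.

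- **Fully missing dates.** A missing start becomes Trial Day 1, provided the stop is later than that day. For stops, "for a missing stop date the date will be imputed as the date of last participation in the trial".
- **Partial dates.** For starts, "If a partial date is missing a start day, '01' will be used for the day", and a missing month becomes January. A stop without a day becomes the last day of its month, and "if a stop date is missing a month 'December' will be used for the stop month". No bound is stated at either end.

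The stated purpose in 7.7 is that "the most conservative case will be considered when assigning medications to categories". Section 7.7.4, within 7.7, summarizes the PDPE antibiotics and refers to 4.2.1 for how they are identified.

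The adverse-event rule in SAP 9.3 does have bounds: "If a partial date is missing a start day and month/year is the same as the date of Treatment Day 1 then use" the Treatment Day 1 date. Partial stops are handled the same way at last participation. SAP 6.3 adds generally: "Missing or partial dates will be resolved in the most conservative manner".

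**The concern.** Two rules in one section treat the same antibiotic in opposite ways. A record with no start date is moved to Trial Day 1 and kept. A record with a known start month, or only a known year, can be moved to before Trial Day 1 and fail the check. More information gives the worse result, and the safeguard that would prevent it already stands in 9.3.

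Days on antibiotics is a gate: under SAP 8.2.3 it must reach p < 0.05 before days in hospital and PDPE rate are tested. If the handling of partial dates is not settled before unblinding, it becomes a choice made within a gated test.

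The gap also affects the stated purpose of 7.7. Section 7.7.3 defines maintained medications as those started before Trial Day 1, so a new antibiotic with such a partial start is tabulated as one the subject was already taking.

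**Working it through.** No figure in the documents depends on this rule, so there is nothing to reproduce. The check applies the rules literally to one constructed record, then to simulated dates.

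**Constructed record.** Randomized 10 March 2015; last participation 15 September 2015; true course 20 March to 2 April, which is 12 + 2 = 14 days.

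| What is recorded | Date used under 7.7 | Item 3 result |
|---|---|---|
| Start fully missing | 10 March | Kept: 22 + 2 = 24 days |
| Start: March 2015 | 1 March, before Trial Day 1 | Fails the check: 0 days |
| Start: 2015 | 1 January, before Trial Day 1 | Fails the check: 0 days |
| Stop: April 2015 | 30 April | 12 + 30 = 42 days, 28 too many |
| Stop: 2015, cap at last participation applied | 15 September | 12 + 30 + 31 + 30 + 31 + 31 + 15 = 180 days, 166 too many |

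The largest error from a missing stop day is 31 − 1 = 30 days (true stop on the 1st of a 31-day month).

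**Simulated dates.** 100,000 records for each true course length of 10, 14 and 21 days. Assumptions, none from the documents except the approximate trial length: randomization dates uniform over two years, 27 weeks of participation, antibiotic starts uniform within participation. All results are per record that already has the stated defect.

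- Start day missing: 8.2% to 8.7% of records are dropped. Those kept gain about 14 days on average.
- Start month missing: 76% to 77% are dropped.
- Stop day missing, true course 14 days: mean count 28.0 days with the cap at last participation.
- Stop month missing, with that cap: mean count 86 to 93 days (89 for a 14-day course).

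The last line matters for the remedy. A ceiling at last participation alone leaves a 14-day course averaging about 89 days.

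**Effect of one record on an arm mean.** SAP section 10 gives 423 randomized, so about 211 per arm if split equally. In crude mean days per subject, one dropped 14-day record is 14/211 = 0.07; the stop-day error above is 28/211 = 0.13; the capped year-only stop is 166/211 = 0.79.

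**The case against.** The strongest reply is that 7.7 does not govern this endpoint. Its stated purpose is category assignment. SAP 6.3 describes the Section 7 date details as concerning safety data, and both 6.3 and 8.2.3 say that missing data for days on antibiotics are not imputed. This stands in part: no readable text says that 7.7 dates enter the duration formula, so that step is an inference. But the Trial Day 1 check is itself a before-or-after assignment, and 7.7.4 applies the 4.2.1 identification inside 7.7. If 7.7 does not apply, no readable rule says how to count days from a partial date. The general instruction in 6.3 to be conservative has no clear direction when two arms are compared.

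A reader might also infer that a year-only stop is counted to 31 December, well past the end of participation. For the constructed record that would be 287 days. The documents do not support this as the likely result. Item 3 substitutes last participation for antibiotics ongoing at that point, and an imputed later stop is most naturally read as ongoing. The supportive count of distinct days uses the same limit. The text does not say that the cap covers imputed stops, so a clarification is still due.

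Collection safeguards are real. Protocol 6.2 requires all antibiotic start and stop dates on the CRF, Protocol 8.2.1.3 requires them in the diary with tracking against clinic and hospital records, and Protocol 13.2 provides for queries. Year-only dates for intravenous courses should be rare. Finally, parts of SAP 8.2.3 and the appendices are redacted, so an endpoint-specific rule may exist there.

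**Conclusion.** The gap holds for starts. The partial-date convention in 7.7 has no floor at Trial Day 1, is inconsistent with the fully-missing rule beside it and with 9.3, and misclassifies antibiotics under 7.7.3. If it is used for item 3, it drops the affected record. For stops the point is narrower: the ceiling is probably present through the ongoing-antibiotic cap but is not explicit, and inflation inside the trial remains.

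The overall size cannot be stated, because the documents give no count of partial antibiotic dates; it is probably small. Two further inferences are not supported. Nothing indicates that partial dates differ between arms, so no directional bias is shown. Nor does one partial date necessarily remove a whole treatment episode, because each antibiotic is a separate record. The exacerbations themselves are identified from the exacerbation review page, so time to first PDPE, PDPE rate and incidence do not depend on this rule.

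The conclusion assumes that 7.7 dates, or an equivalent convention, are used in item 3 and that no redacted text overrides them.

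**What to change.** State in SAP 7.7 and 4.2.1 item 3, before unblinding, that for antibiotics linked to a PDPE:

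- a partial start is the latest of Trial Day 1, the linked PDPE start date and the first day of the recorded month or year;
- a partial stop is the earliest of the last day of the recorded month or year, the linked PDPE end date (if recorded) and last participation, and never before the start.

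The PDPE end date is needed because last participation alone leaves most of the within-trial inflation. SAP 4.2.1 item 4 already relies on PDPE dates to classify hospitalizations. If Trial Day 1 or a linked PDPE date falls outside the recorded month or year, query the record rather than move it.

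For other medications, use bounds in the style of 9.3: Trial Day 1 when the recorded month or year matches it, and last participation for stops. List every imputed antibiotic date.

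The cost is two sentences in the SAP and a small change to one derivation.
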